1.1 Hormone-refractory Prostate Cancer

Prostate cancer has high global incidence and mortality. Approximately one in every nine men in North America will be diagnosed with prostate cancer during his lifetime. It is the most common malignancy and the second most common cause of cancer death in North American males. Worldwide, prostate cancer ranks third in cancer incidence and sixth in cancer mortality among men (1).

The course of prostate cancer from diagnosis to death is categorized as a series of clinical states defined by the extent of disease, hormonal status, and absence or presence of detectable metastases on an imaging study. The states are localized disease, rising prostate specific antigen (PSA) after local therapy with radiation therapy or surgery, advanced disease with clinical metastases that initially respond to androgen ablation therapy, and advanced disease that progresses in the presence of androgen deprivation. PSA is a widely used marker of disease progression and response to treatment changes in PSA foretell subsequent changes in radiographic evidence of metastases. The states are recognized by patients and physicians and allow a clear definition of therapeutic objectives and outcomes.

1.2 Background

Advanced Prostate Cancer is associated with prostate cancer-specific mortality and much of the morbidity of the disease. The most common site of metastasis is to bone with 80% of patients dying from the disease having bone metastasis. Skeletal metastasis may result in bone pain, fractures and bone marrow failure. Vertebral involvement may create even more morbidity from spinal cord compression, which if left untreated may result in paralysis.

The androgen receptor (AR) is the primary oncogenic driver of prostate cancer, and the first line of therapy of advanced disease is androgen deprivation, historically by surgical orchiectomy and more commonly, by suppression of the pituitary-gonadal axis with luteinizing hormone releasing hormone (LHRH) analogues. Second line hormonal therapy, by targeting the androgen receptor, has shown a tumor response in less than half of castrate patients. This response is not durable, with median duration of response approximating 7 months. (2) When prostate cancer develops resistance to castration and anti-androgen combinations, a decrease in PSA may be obtained by withdrawing anti-androgen therapy. The withdrawal response rate, however, is no higher and the duration of response even shorter than other second-line hormonal therapies.

After the failure of hormonal therapies, chemotherapy may palliate the symptoms of prostate cancer for those patients who can tolerate the side effects. Docetaxel confers a survival advantage for patients with hormone-refractory prostate cancer, with a median survival of 18 months. Nonetheless, current treatment for advanced prostate cancer is not curative and the

optimal time of administration of chemotherapy remains under active study. Newer agents include Provenge (Sipuleucel-T) a vaccine made from the patient's own cells primed to the prostate specific membrane antigen and re-administered to the patient. As well Abiraterone acetate a CYP17 lyase inhibitor has been shown to increase overall survival in the post chemotherapy setting. In addition Xtandi another androgen receptor blocking agent is available in the post- docetaxel setting.

Xofigo (radium 223) was recently approved in the metastatic castrate resistant prostate cancer patient with symptomatic bone metastasis. In the phase III study time to first SRE, overall survival in the xofigo arm was improved as well, time to total ALP progression, time to PSA progression and a total alkaline phosphatase response was statistically significantly longer in the radium-223 chloride group compared to placebo (see below for statistical details).

In summary, the current natural history of advanced prostate cancer is comprised of one to several years of response to androgen deprivation, several months of response to secondary hormonal therapies, and subsequently cytotoxic chemotherapy for a remaining median survival time of less than two years. There is a medical need to extend the rate and duration of response for chemotherapy while understanding pathways that confer sensitivity or resistance in individualized patients.

1.3 Rationale of the study

Based upon the Radium 223, Alpharadin, phase III trial which has been shown to not only palliate pain but also shown to increase overall survival as compared to placebo (median OS 14.9 months versus 11.3 months) in CRPC without decreases in PSA we propose this study to further understand the mechanism of Radium-223 and its effects within the tumor microenvironment in bone.

These observations outlined above on changes in alkaline phosphatase without significant decreases in PSA are consistent with the hypothesis that targeting the bone microenvironment (osteoblast and/or osteoclast) is implicated in CRPC progression and provides rationale for determining stromal-tumor interactions when exposed to alpharadin.

1.3.1 Pharmacokinetics / pharmacodynamics

Pharmacodynamics within the tumor microenvironment will be determined through sampling of the bone marrow biopsy and aspirates as well as serum/plasma. Please see below for details.

No pharmacokinetics will be performed.

1.4 Ra-223 dichloride

Mechanism of Action

Radium-223 dichloride is a therapeutic alpha particle-emitting pharmaceutical with targeted anti-tumor effect on bone metastases. Ra-223 dichloride mimics calcium and selectively targets bone, specifically areas of bone metastases, by forming complexes with the bone mineral hydroxyapatite. The high linear energy transfer of alpha emitters (80 keV/micrometer) leads to a high frequency of double-strand DNA breaks in adjacent cells, resulting in a potent and localized anti-tumor effect. The alpha particle range from radium-223 is less than 100 micrometers (less than 10 cell diameters) which minimizes damage to the surrounding normal tissue.

Preclinical

In single and repeated dose toxicity studies in rats, the main findings were reduced body weight gain, hematological changes, reduced serum alkaline phosphatase and microscopic findings in the bone marrow (depletion of hematopoietic cells, fibrosis), spleen (secondary extra-medullary hematopoiesis) and bone (depletion of osteocytes, osteoblasts, osteoclasts, fibro-osseous lesions, disruption/disorganization of the physis/growth line). These findings were related to radiation-induced impairment of hematopoiesis and a reduction of osteogenesis and occurred beginning in the dose range of 20 (0.00056 mCi) – 80 kBq (0.0022 mCi) per kg body weight, with the exception of body weight decreases.

Dose-limiting myelotoxicity was seen in dogs after single administration of 450 kBq (0.012 mCi) Ra-223 dichloride per kg body weight (9 times the clinically recommended dose).

Osteosarcomas, a known effect of bone-seeking radionuclides, were observed at clinically relevant doses in rats 7 – 12 months after start of treatment. Osteosarcomas were not observed in dog studies. The presence of neoplastic changes, other than osteosarcomas, was also reported in the longer term (12 to 15 months) rat toxicity studies. Due to its mode of action, and as seen with conventional radiotherapy and other radiotherapeutics, radium-223 dichloride may have the potential to induce secondary malignancies. No case of osteosarcoma has been reported in clinical studies with Ra-223 dichloride. The risk for patients to develop osteosarcomas with exposure to Ra-223 dichloride is unknown at present

Studies on reproductive and developmental toxicity have not been performed. Since Ra-223 dichloride binds to bone, the potential risk for toxic effects in the male gonads in cancer patients with castration-resistant prostate cancer is very low, but cannot be excluded. Studies on the mutagenic and carcinogenic potential of Ra-223 dichloride have not been performed.

No histological changes were observed in organs involved in the excretion of Ra-223 dichloride. No significant effects were seen on vital organ systems, i.e. cardiovascular (dog), respiratory or

central nervous systems (rat), after single dose administration of 450 to 1000 kBq (0.012 to 0.027 mCi) per kg body weight (9 (dog) to 20 (rat) times the clinically recommended dose.

Clinical Experience Summary

The clinical development of Ra-223 dichloride includes phase I and phase II studies in prostate cancer patients with bone metastases. The results of these completed studies indicated that safety and tolerability of Ra-223 dichloride in CRPC/HRPC patients with bone metastases was well tolerated, and that there was evidence of dose related efficacy against bone markers and other markers of disease. In addition there was an effect on median overall survival in a Phase II (BC1-02) placebo-controlled study. These studies enabled the initiation of the Phase III ALSYMPCA (ALpharadin in SYMptomatic Prostate CAncer) study.

The clinical safety and efficacy of Ra-223 dichloride have been evaluated in a double-blind, randomized, multiple dose, phase III multicenter study (ALSYMPCA) in castration-resistant prostate cancer patients with bone metastases. The primary efficacy endpoint was Overall Survival (OS).

At the cut-off date of the pre-planned interim analysis, a total of 809 patients were randomized 2:1 to receive Ra-223 dichloride 50 kBq (0.0014 mCi)/kg intravenously every 4 weeks for 6 cycles (N=541) plus best standard of care or matching placebo plus best standard of care (N=268). Best standard of care included (e.g. local external beam radiotherapy, corticosteroids, antiandrogens, estrogens, estramustine or ketoconazole).

An updated descriptive analysis of safety and of OS was performed in 921 randomized patients prior to implementing crossover (i.e. offering patients in the placebo group to receive Ra-223 dichloride treatment).

The results of both, interim and updated analysis, revealed that OS was significantly longer in patients treated with Ra-223 dichloride plus best standard of care compared to patients treated with placebo plus best standard of care. For the updated analysis, an increase in median overall survival of 3.6 months was seen with Ra-223 dichloride plus best standard of care compared to placebo plus best standard of care (HR =0.695 (95% CI 0.581/0.832), median OS 14.9 months versus 11.3 months, respectively).

In the ALSYMPCA study, the results of the interim analysis and the updated analysis showed also a significant improvement in all main secondary endpoints in the Ra-223 dichloride arm compared to the placebo arm:

Time to first SRE (defined as time to EBRT, time to first pathological bone fracture, time to spinal cord compression and time to surgical intervention) was statistically significantly longer in

the radium-223 chloride group compared to placebo (median number of months=15.6 for radium-223 chloride versus 9.8 months for placebo (HR=0.658, 95 CI 0.522–0.830, p= 0.00037).

Time to total ALP progression (defined as $\geq 25\%$ increase compared to baseline/nadir) was statistically significantly longer in the radium-223 chloride group 7.4 months compared to placebo 3.8 months (HR = 0.167, 95% CI 0.129 – 0.217; p= <0.00001).

Time to PSA progression (defined as a $\geq 25\%$ increase and an increase in absolute value of ≥ 2 ng/mL compared to baseline/nadir) was also significantly prolonged in patients receiving Ra-223 dichloride compared to patients receiving placebo (HR = 0.643, 95% CI 0.539,0.768; p = <0.00001).

A total ALP response (defined as a confirmed $\geq 30\%$ or $\geq 50\%$ reduction compared to baseline) at week 12 was observed in higher proportions of subjects who were treated with radium-223 chloride group (47% and 3% respectively) compared to those in the placebo (3% and <1% respectively) group.

Subgroup survival analysis showed a consistent survival benefit for treatment with Ra-223 dichloride, independent of total alkaline phosphatase (ALP), current use of bisphosphonates, prior use of docetaxel and baseline ECOG status. The results from the phase III ALSYMCA study regarding time to external beam radiation therapy (EBRT) for pain relief and fewer patients reporting bone pain as an adverse event in the Ra-223 dichloride group indicate a positive effect on bone pain.

Most common hematologic adverse events all grades were anemia (31.2%), neutropenia (5%) and thrombocytopenia (11.5%). Most common non-hematologic all grades adverse events occurring in more than 15% of patients were: bone pain, diarrhea, nausea, vomiting and constipation.

Table 1 shows adverse reactions occurring in $\geq 1\%$ of patients and for which the rate for Ra-223 dichloride exceeds the rate for placebo.

System/Organ Class Preferred Term	Ra-223 dichloride (n=600)		Placebo (n=301)	
	All Grades %	Grades 3-4 %	All Grades %	Grades 3-4 %
Blood and lymphatic system disorders				
Thrombocytopenia	11.5	6.3	5.6	2
Neutropenia	5	2.2	1	0.7
Leukopenia	4.2	1.3	0.3	0.3
Pancytopenia	2	1.2	0	0
Gastrointestinal disorders				
Diarrhea	25	1.5 (grade 3 only)	15	1.7 (grade 3 only)
Vomiting	18.5	1.7 (grade 3 only)	13.6	2.3 (grade 3 only)
Nausea	35.5	1.7 (grade 3 only)	34.6	1.7 (grade 3 only)
General disorders and administration site conditions				
Injection site reactions (including erythema, pain and swelling)	1.2	0	0	0

*Adverse reactions are identified using MedDRA version 14.1 and graded according to CTCAE version 3.0.

*An additional clinically important adverse reaction observed in less than 1% of <PTN>-treated patients and at a higher incidence than in placebo-treated patients was lymphopenia (0.8% vs. 0.3%).

Secondary Malignant Neoplasms

No cases of radiation-induced cancer have been reported in reported in clinical trials with radium-223 dichloride in follow-up of up to three years. However, the radiation dose resulting from therapeutic exposure may result in higher incidence of cancer (e.g. sarcomas of the bone, or leukemia), mutations and a potential for development of hereditary defects.

2. Study objectives

Primary Objective:

- To identify markers of both predictive and prognostic importance within bone marrow biopsies, aspirates as well as serum in patients with metastatic CRPC to bone, to be treated with the standard 6 doses of Alpharadin.

[figure not shown]
Secondary Objectives:

- Link PSA initial concentration (as defined within PCWG2) to modulation of bone markers, in the blood, urine and bone marrow plasma of study patients
- Estimate the efficacy and PFS by PCWG2 in study patients
- Develop a deeply annotated tissue repository for later hypothesis generating associations
- Correlative studies in prostate cancer patient-derived mouse models to validate predictive and prognostic biomarker associations (SEE APPENDIX E)
- To estimate the overall survival in patients with CRPC

3. Study design

This is an open label study to determine the effect of Alpharadin on the bone marrow microenvironment in patients with CRPC and bone metastases. We will determine the modulation of bone microenvironment as measured by serum, plasma, urine and bone marrow aspirate bone markers. The baseline determination and subsequent assessment of bone-prostate cancer paracrine signaling will be correlated with PSA decline, progression free survival, overall survival and changes in pain indices.

Subjects will be treated with the standard dosing of xofigo (Alpharadin) Ra-223 dichloride 50 kBq (0.0014 mCi)/kg intravenously every 4 weeks for 6 cycles (6 doses total).

For pharmacodynamic effects: tumor/osteoblast/osteoclast along with Ki-67 (proliferation marker), gamma H2AX (DNA double strand breaks), and cleaved PARP. Co-localization by immunohistochemistry for cytokeratin/PSA for tumor cells, BALP for osteoblasts, and TRAP staining for osteoclasts on bone marrow core samples. This will be performed at pre-treatment, week 12 and week 24.

For plasma markers (peripheral blood) indicative of bone formation and degradation this panel will be performed at baseline, week 12, week 16 and week 24: ALP (alkaline phosphatase) BALP* (bone alkaline phosphatase), OPG (osteoprotegerin), RANKL (receptor activator of nuclear factor-B ligand), OPN (osteopontin), OC (osteocalcin), CTX (c-telopeptide-collagen), PINP* (n-terminal propeptide of type 1 procollagen),

Bone secreted factors in the bone marrow aspirate that reflect the status of osteoblasts or osteocytes

1. Alkaline phosphatase--osteoblasts
2. Osteocalcin—both osteoblasts and osteocytes
3. DMP (Dentin matrix acidic phosphoprotein 1)
4. Sclerostin markers of osteocytes

Bone secreted factors that modulate tumor cell activity and tumor cell response to therapies

1. Tenascin—activate integrins
2. Periostin—activate integrins
3. Lumican—active integrins
4. Decorin—binding to EGFR, IGFR, MET, class A scavenger receptor (SR-A)
5. Osteopontin-binding to CD44 and integrins
6. Osteonectin—activate integrins
7. Nidogen-1—activate integrins
8. TGFb-induced protein ig-h3—activate integrins

Urine: NTx (n-terminus cross-linking telopeptide) a marker of osteoclast activity.

We will then assess selected factors in the blood and bone marrow aspirates of the treated patients and will correlate the factors with changes in serum bone specific alkaline phosphatase levels and objective clinical evidence of response to therapy. Our correlative studies will expand on the use of the bone markers outlined above in developed patient-derived xenografts (PDXs) that mimic the heterogeneity of bone-metastatic CRPC (SEE APPENDIX E FOR EXPERIMENTAL APPROACH AND TIMELINE). Together, our clinical and mouse model studies will be performed with the objective of identifying novel factors, early predictors of response to Alpharadin that would guide in the further development and possible earlier use of

Alpharadin or other novel alpha emitters as a therapy for CRPC. These correlations will be conducted using descriptive statistics.

4. Study Population

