10.5 Primary Objective Exploration

Each marker will be tested individually using a Cox regression model to determine whether it is associated with overall survival. Markers measured on a continuous or ordinal scale will be included with their original units in the model. First, the baseline values will be used to determine if the baseline is associated with survival. Next we will calculate the percent change from baseline and use that as a continuous measure in the model. The ordered category of reduced by 30%, same, or increased by 30% grouping will be used in the model. Finally, all observed values of the marker will be included as a time-varying covariate in the Cox regression model. Since this is an observational study to identify potential usefulness of biomarkers in predicting overall survival, no formal adjustments for multiple testing will be needed for future trial planning. However, for publication, only markers with a significance level of ≤ 0.002 will be considered meaningful in predicting survival. This is based on a Bonferroni correction of approximately 25 markers of interest. Additional regression-tree style partitioning may be performed to identify potentially meaningful cutpoints for combinations of markers. Cutpoints will be examined together with demographic and medical status variables. This will be purely exploratory and will need to be confirmed in an independent data set in a future trial.

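### The primary objective asks for predictive markers, but with every patient on Ra-223 the OS and PFS models can show only association under treatment

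*Combined protocol and SAP*

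**What the plan says.** Section 2 (Primary Objective) asks for two properties, named separately: "To identify markers of both predictive and prognostic importance within bone marrow biopsies", and likewise in aspirates and serum.

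Section 3 describes an open-label study with a single regimen: "Subjects will be treated with the standard dosing of xofigo (Alpharadin) Ra-223 dichloride 50 kBq (0.0014 mCi)/kg intravenously every 4 weeks for 6 cycles". Section 5 repeats it. No control group, randomisation scheme or external comparator is described. The word randomized appears in the dropout definition of Section 9.1, but nothing else in the document supports it.

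The primary analysis is in Section 10.5: "Each marker will be tested individually using a Cox regression model to determine whether it is associated with overall survival". Each marker enters as a baseline value, as percent change, as a three-level 30% category, and lastly over time: "Finally, all observed values of the marker will be included as a time-varying covariate in the Cox regression model". Section 10.6 carries similar analyses over to PFS. No model contains a treatment term. Section 10.8 gives power for a marker's own association with survival and for nothing else.

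Section 3 also plans descriptive correlations with bone-specific alkaline phosphatase and clinical response. It gives the joint aim of the patient and mouse work as "identifying novel factors, early predictors of response to Alpharadin", to inform later development and possibly earlier use of the drug.

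**The concern.** A prognostic marker is associated with outcome whatever the treatment. A predictive marker changes the size of the treatment effect, so it is defined by a contrast between treated and untreated patients at different marker values. Section 2 claims both properties, and the patient-level design supplies data for only one side of that contrast.

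What is at stake is the conclusion the trial may draw. A marker that passes the 0.002 publication threshold in 10.5 could be reported as meeting the primary objective, and so as predictive, when the analysis cannot tell it from a marker of poor outlook.

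The protocol's own background gives an example. Section 1.4 reports that the survival benefit in the randomised phase III trial was consistent irrespective of total ALP, a statement that needed the placebo arm. ALP is also on this trial's serum marker list (Section 10.2). If ALP is associated with OS here, the objective as worded would allow it to be called predictive, and nothing in 10.5 could contradict that.

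**Working it through.** **1. Reproduce the plan's figure.** Inputs from Section 10.8: 25 patients, 80% power, two-sided 5%, HR 1.57 per unit with SD 1.25, and HR 1.45 with SD 1.5. For a continuous covariate in a Cox model,

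D = (z₀.₉₇₅ + z₀.₈₀)² / (SD² × ln(HR)²), with (1.960 + 0.842)² ≈ 7.849.

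- HR 1.57, SD 1.25: 7.849 / (1.5625 × 0.2035) = 24.7 deaths; power with 25 deaths is 80.5%.
- HR 1.45, SD 1.5: 7.849 / (2.25 × 0.1381) = 25.3 deaths; power with 25 deaths is 79.6%.

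The figure reproduces if all 25 patients die. It is power for a marker main effect among treated patients.

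**2. What the planned models estimate.** Let M be the marker and T = 1 for Ra-223, 0 otherwise. A model that could address both halves of the objective is

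log hazard ratio = β_T·T + β_M·M + β_TM·T·M,

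where β_M is the prognostic effect and β_TM the predictive one. Here T = 1 for everyone, so T·M equals M and the model reduces to (β_M + β_TM)·M. The columns M and T·M have rank 1 instead of 2, so only the sum is estimable.

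**3. Two explanations, one likelihood.** Take the plan's HR of 1.57, ln(1.57) = 0.451:

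| | β_M | β_TM | HR per unit, untreated | HR per unit, treated | Interaction ratio |
|---|---|---|---|---|---|
| Purely prognostic | 0.451 | 0 | 1.57 | 1.57 | 1.00 |
| Purely predictive | 0 | 0.451 | 1.00 | 1.57 | 1.57 |

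Only the treated column is observed, so the Cox partial likelihood is the same in both rows for any number of patients. The same algebra applies to PFS and to every marker coding. For on-treatment change there is a further gap: without controls, change caused by Ra-223 cannot be separated from natural course or from the concomitant prostate cancer treatments that Section 6.1 says may be recorded.

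**4. Information on the interaction.** With treated share p, the events needed for β_TM are 7.849 / (p(1−p) × SD² × ln(HR)²). At p = 1 the denominator is 0 and no number of deaths suffices.

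For scale only, assume a control arm, an interaction ratio of 1.57 and SD 1.25:

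- 1:1 allocation: 7.849 / (0.25 × 1.5625 × 0.2035) ≈ 98.8, so 99 deaths.
- 2:1 allocation: 7.849 / (0.2222 × 1.5625 × 0.2035) ≈ 111.1, so 112 deaths.
- 25 deaths at 1:1: power about 29%.

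Adding a small control group to this trial would therefore not rescue the predictive half.

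**The case against.** **The study is exploratory.** Section 10.5 says "Since this is an observational study to identify potential usefulness of biomarkers in predicting overall survival", and Section 10.8 calls all findings preliminary. These caveats lower the risk of premature use and are a reason to keep the remedy modest. They concern chance and small numbers, however, and the problem here is identifiability. The independent data set that 10.5 asks for, in connection with cutpoints, need not have a comparator. A second all-treated cohort would repeat the ambiguity.

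**Predictive may be meant loosely.** The document never defines the word, and Sections 10.4 and 10.5 use predict in its everyday sense. That is possible. But Section 2 sets predictive beside prognostic, so the technical reading is fair. If the loose sense was meant, the objective repeats itself and needs the same clarification.

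**Response is a different outcome from survival.** This stands, and it limits the point. A reader might infer that the trial carries no information at all about drug effect. That goes too far. Section 1.4 gives a week-12 total ALP reduction of at least 30% in 47% on Ra-223 and 3% on placebo. If a similar 3% applied here, then in a marker group holding half the patients the untreated response rate could be at most 3% / 0.5 = 6%. A large difference in ALP response between marker halves would then say something about drug effect on that endpoint. It would rest on a borrowed control rate, it is planned as description only, and it would not show survival benefit.

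**The mouse work may have controls.** This also stands. Appendix E is not in the supplied text, so untreated animals cannot be ruled out. A reader might infer that the word predictive should also go from the mouse-model secondary objective. The all-treated argument concerns the patients and does not support that. Equally, animal controls would not give a patient-level interaction.

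**Conclusion.** The point holds for the patient-level OS and PFS analyses. As written, Section 2 assigns them a property they cannot deliver: the marker-by-treatment effect is not estimable at any sample size, while the association under treatment is estimable and is what Section 10.8 powers. This rests on two readings: that predictive means effect modification, and that no comparator exists outside the supplied text.

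A reader might also infer that the protocol intends to select patients with these markers. Section 3 does not say so. It speaks of guiding development and possible earlier use. The harm to name is a prognostic association carried into that work as if it showed who benefits.

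The change is worth making because it alters what the trial may conclude. The planned prognostic and pharmacodynamic work remains usable.

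**What to change.** - **Section 2, primary objective:** restate it at patient level, for example: to identify baseline markers and on-treatment marker changes associated with overall survival (prognostic and pharmacodynamic) in patients treated with Ra-223.
- **Section 10.5, applying also to 10.6:** add that the OS and PFS models show association under Ra-223 only, and that a predictive claim needs a study with a non-Ra-223 comparator.
- **Section 3:** state that correlations with response are descriptive associations in treated patients and do not establish prediction of survival benefit from Ra-223. Keep response distinct from survival.
- **Section 2, mouse-model objective:** leave it in place, labelled as preclinical and hypothesis-generating.

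No patients, samples, visits or analyses are added. The cost is a stated aim that is slightly less ambitious.
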